5. AMENDMENTS AND UPDATES

Version Identifier	Date	Amendment Type (substantial or administrative)	Protocol Section(s) Changed	Summary of Amendment(s)	Reason
V 2.0	06 August 2025	Substantial	Abstract	The study end date and corresponding data availability period were updated. Two additional interim analyses were added.	The study period was extended to increase sample size and follow-up time for analysis.
V 2.0	06 August 2025	Substantial	Milestones	The study end date and corresponding data availability period were updated. Two additional interim analyses were added.	Same as above
V 2.0	06 August 2025	Substantial	Study Design	The end date for data availability was changed from March 2025 to December 2025.	Same as above
V 2.0	06 August 2025	Substantial	Data Source	The study end date and corresponding data availability period were updated. Two additional interim analyses were added.	Same as above

V 2.0	06 August 2025	Substantial	ANNEX 2. ADDITION AL INFORMA TION	HCPC codes for IV antibiotics were added to the 'Antibiotics' section	Additional HCPC codes for IV Anti-Infectives were identified and added to the overall Antibiotics category
V 2.0	06 August 2025	Substantial	Data Analysis	Added mandatory template text about separate SAP.	Separate SAP was be developed.
V 2.0	06 August 2025	Substantial	Title page	Active substance and Medicinal product rows	Updated to match Pfizer template requirement.
V 2.0	06 August 2025	Substantial	9.6.1. Case Report Forms/Data Collection Tools/Electr onic Data Record and 9.6.2. Record Retention	Sections 9.6.1 and 9.6.2 removed.	Per template instructions: Sections 9.6.1 and 9.6.2 should be deleted for studies with no human review of unstructured data; these are studies in which either of the following occurs: • All study data exist as structured data by the time of study start • The conversion of unstructured data to structured data during the implementation of the protocol is performed solely by a computer using automated/algorithm ic methods, such as natural language processing.
V 2.0	06 August 2025	Substantial	List of Abbreviatio ns	Abbreviations added	AE, EC, ESRD, CMS, SAP and VRDC were missing

V 2.0	06 August 2025	Substantial	Setting	Added the following blurb for Figure 1: "The data end date in Figure 1 will be updated at the time of the second, third, and final analyses, estimating data through June, September, and December 2025, respectively. All other dates shown in the figure will remain the same for the subsequent analyses"	This clarification was needed because of milestones change.
V 2.0	06 August 2025	Substantial	Annex 2	Code J9415 changed to J9145	while reviewing codes it was noticed a typo in the 'CD38 mAbs' and 'mAbs' codes under Annex 2. It looks like the code J9415 should actually be J9145 for Daratumumab.

6. MILESTONES

Milestone	Planned Date
Start of data collection	25 October 2024
Interim study report	18 December 2024
First interim analysis based on data through December 2024	25 June 2025
Second interim analysis based on data through June 2025	30 September 2025
Third interim analysis based on data through September 2025	19 December 2025
End of data collection	31 December 2025
Final analysis based on data through December 2025	27 February 2026
Final study report	8 May 2026

7. RATIONALE AND BACKGROUND

Multiple myeloma (MM) is a hematological malignancy originating in plasma cells in the bone marrow.^{1,2} Healthy plasma cells secrete antibodies, also known as immunoglobulins, to fight infection and act as the humoral line of defense.^{1,2} Plasma cells that have become cancerous (i.e., myeloma cells) proliferate and displace normal cell production in bone marrow, among other effects on the immune system. As a consequence, the general production of antibodies is impaired, decreasing the body's supply of antibodies.³ MM is characterized by an increase in non-functional monoclonal proteins (M proteins), a decrease in blood count, renal failure, end-organ damage, susceptibility to infections, and bone weakness.^{1–3} The incidence of MM was 7.4 per 100,000 people in the United States (US) from 2016-2020, while the 5-year relative survival from 2013 to 2019 was 59%.⁴ MM is the second most prevalent hematological malignancy and accounted for approximately 1.8% of all new cancer cases in 2023.^{5,6}

Many therapies for MM exist, and clinical advances continue to change the treatment landscape. The advent of therapies, such as proteasome inhibitors (PIs), immunomodulatory drugs (IMiDs), and monoclonal antibodies (mAbs), has increased the overall survival of MM patients. ^{7–9} Despite numerous advances in the available therapies for MM, most patients with MM will either relapse (fail to respond to treatment) or become refractory (have their treatment fail). ¹⁰ These patients are collectively referred to as having relapsed or refractory multiple myeloma (RRMM). Given relapse to later lines confers progressively worse outcomes including shorter survival time, there is a need to investigate alternative treatment options in this setting. ^{9,10}

Recent improvements in treatment for patients with RRMM included advances in B-based treatments targeting B-cell maturation antigen (BCMA), which is primarily present in malignant plasma cells. BCMA is expressed in B-cells and regulates their maturation into plasma cells. BCMA bispecific antibodies (BsAb) target and bind BCMA-expressing plasma cells and the CD3 receptor on T-cells, activating cytotoxic activities of the T cell. Elranatamab is approved in the US for patients who have received at least four lines of therapy, including a PI, an immunomodulatory agent, and an anti-CD38 mAbs. 12

Teclistamab, another BCMA BsAb, was approved in October 2022, based on results from the MajesTEC-1 trials; the ORR was 63.0%, and common adverse events included infections (76.4%), cytokine release syndrome (72.1%), anemia (52.1%), and neutropenia (70.9%). Elranatamab was approved in August of 2023, based on the results from the MagnetisMM-3 trial, a phase 2 trial aimed at assessing the efficacy of elranatamab monotherapy. The ORR was 61.0%, and common adverse events included infections (69.9%), cytokine release syndrome (57.7%), anemia (48.8%), and neutropenia (48.8%). While some published studies have assessed the real-world utilization of other BCMA BsABs such as teclistamab, the real-world usage of elranatamab has not been characterized. This study aims to describe the uptake and use of elranatamab subsequent to the August 2023 Food and Drug Administration (FDA) approval.

This noninterventional study is designated as a PASS and is conducted voluntarily by Pfizer.

8. RESEARCH QUESTION AND OBJECTIVES

The overall aim of the study is to understand the real-world usage of elranatamab for the treatment of MM. To meet these objectives, the Clarify team will partner with Pfizer to create a curated dataset of Medicare FFS beneficiaries and their treatments to serve as the foundation upon which to examine descriptive data.

Specifically, the analysis will focus on the following primary research objectives:

Primary

- **Objective 1:** To describe the demographics, clinical history, and treatment history of patients treated with elranatamab
- Objective 2: To describe the administration and treatment management of elranatamab
 - Assess administration and management details (place of service, dosage, timing, frequency, supportive MM medication usage)
 - Evaluate dose, duration, and reasons for administration interruption or discontinuation, as available
- **Objective 3:** To describe all-cause and MM-related healthcare resource utilization (HCRU) and associated costs among patients treated with elranatamab

Exploratory

- Exploratory Objective 1: To describe the tolerability and real-world safety of elranatamab
- Exploratory Objective 2: To describe the overall effectiveness of elranatamab in terms of
- time to next treatment or death (TTNT/D) and overall survival (OS)
- Exploratory Objective 3: In a separate cohort, replicate all objectives for patients who initiated teclistamab

9. RESEARCH METHODS

9.1. Study Design

This will be a retrospective, non-interventional descriptive cohort study using de-identified patient data from US-based Medicare Fee for Service (FFS) beneficiaries. The study will utilize claims data from the Centers for Medicare and Medicaid Services (CMS), spanning from 2016 through December 2025.

9.2. Setting

This study will evaluate adult patients with RRMM who initiate elranatamab or teclistamab. Patients will enter (i.e., index) on the first observed elranatamab or teclistamab claim between August 14, 2023 and March 2025. Limited eligibility criteria will be applied.

Study Period: Start of data (Jan 1, 2016) to the most current, available data.

MM diagnosis window: Start of data (Jan 1, 2016) to index date

Index date: First elranatamab or teclistamab claim after initial MM diagnosis

Observability: At least 180 days of continuous closed-claims medical and pharmacy enrollment prior to index (inclusive) and 30 days after the index date

Baseline period for MM-related treatments and MM-related comorbidities: MM diagnosis to one day prior to index date

Charlson Comorbidity Index and baseline HCRU assessment window: 180 days prior to index date to index date

Follow-up: Index date until death, the earliest of end of study period, or end of continuous enrollment (unless otherwise noted). Alternative censoring criteria will be applied for certain outcomes (such as OS, TTD, and TTNT/D).

Figure 1 reflects the time periods of interest in the study cohort. The data end date in Figure 1 will be updated at the time of the second, third, and final analyses, estimating data through June, September, and December 2025, respectively. All other dates shown in the figure will remain the same for the subsequent analyses.

[figure not shown]

Figure 1. Study Schematic for Patients Receiving Elranatamab or Teclistamab

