9.2.1. Inclusion Criteria

Patients must meet all of the following inclusion criteria to be eligible for inclusion in the study:

- At least 1 observed prescription claim or medical claim for elranatamab or teclistamab in the
 dataset between August 14, 2023, and the most current date of data available. The index date will
 be the date of an individual's first claim. Patients who have received teclistamab before the
 August 14, 2023, date will require a period (i.e., 6 or 12 months) without a claim for teclistamab.
- 2. Age 18 or older on index date

- 3. Diagnosis of RRMM (defined as MM) any time prior to index date
- 4. At least 180 days of continuous closed-claims medical and pharmacy enrollment prior to index (inclusive) and 30 days post-index

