1	Care setting	Categorical care setting for elranatamab or teclistamab administration Inpatient (IP) Non-IP Pharmacy	Index date, second treatment date, third treatment date, and overall

Objective	Variable	Definition	Assessment Period(s)
1	Time since MM diagnosis	Time (in months) from first MM diagnosis to index date (continuous)	MM diagnosis to index date
1	Income	Categorical household income	Index date
1	Education	Categorical level of highest education completed:	Index date
1	Marital Status	Categorical marital status:	Index date
1	Home Ownership	Categorical home ownership status: Renter Owner Unknown	Index date
1	Triple class exposed ¹⁷	 Medical claim in the IP, Non-IP or pharmacy setting with an NDC, HCPCS, Current Procedural Terminology (CPT), generic name, or ICD-10 procedure code for all the following therapies in the inpatient, non-IP, or pharmacy setting (dichotomous): ≥ 1 claim for PIs (see generic names below) ≥ 1 claim for IMiDs (see generic names below) ≥ 1 claim for CD38 mAbs (generic names: daratumumab, isatuximab) 	MM diagnosis to 1 day prior to index date
1	Penta-drug exposed ¹⁷	Medical claims with an NDC, HCPCS, CPT, generic name, or ICD-10 procedure codes in the inpatient, non-IP or pharmacy setting for all of the following therapies(dichotomous): • ≥ 2 distinct claims for PIs (see generic names below) • ≥ 2 distinct claims for IMiDs (see generic names below) • ≥ 1 claim for CD38 mAbs (generic names: daratumumab, isatuximab)	MM diagnosis to 1 day prior to index date

Objective	Variable	Definition	Assessment Period(s)
1	Hematopoietic Stem Cell Transplantation	Medical claim with an HCPCS, CPT, or ICD-10 code for hematopoietic stem cell transplantation in the inpatient, non-IP setting (dichotomous)	MM diagnosis to 1 day prior to index date
1	BCMA-directed therapy	Medical claim with an NDC, HCPCS CPT, generic name or ICD-10 procedure code in the inpatient, non-IP, or pharmacy setting for idecabtagene vicleucel, ciltacabtagene autoleucel, or belantamab (dichotomous)	MM diagnosis to 1 day prior to indexhe date Index date to the end
			of follow-up
1	CAR-T	Medical claim with an NDC, HCPCS, generic name or CPT code in the inpatient, non-IP, or pharmacy setting for idecabtagene vicleucel or ciltacabtagene autoleucel (dichotomous)	MM diagnosis to 1 day prior to index date
		autoreucer (dienotomous)	Index date to the end of follow-up

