1	Talquetamab	Medical claim with an NDC, HCPCS, generic name or CPT code in the inpatient, non-IP, or pharmacy setting for talquetamab (dichotomous)	MM diagnosis to 1 day prior to index date
			Index date to the end of follow-up
1	PIs	Medical claim with an NDC, HCPCS, generic name or CPT code in the inpatient, non-IP, or pharmacy setting for bortezomib, carfilzomib, or ixazomib	MM diagnosis to 1 day prior to index date
		(dichotomous)	Index date to the end of follow-up
1	IMiDs	Medical claim with an NDC code or generic name in the non-IP or pharmacy setting for lenalidomide, thalidomide, or pomalidomide (dichotomous)	MM diagnosis to 1 day prior to index date
			Index date to the end of follow-up
1	Steroids	Medical claim with an NDC, HCPCS, generic name or CPT code in the inpatient, non-IP, or pharmacy setting for dexamethasone, methylprednisolone, prednisone, or prednisolone (dichotomous)	MM diagnosis to 1 day prior to index date
		prediffication, or prediffication (dieffotolificas)	Index date to the end of follow-up

Objective	Variable	Definition	Assessment Period(s)
1	mAbs	Medical claim with an NDC, HCPCS, generic name or CPT code in the inpatient, non-IP, or pharmacy setting for daratumumab, isatuximab, or elotuzumab (dichotomous)	MM diagnosis to 1 day prior to index date
			Index date to the end of follow-up
1	Chemotherapies	Medical claim with an NDC, HCPCS, generic name or CPT code in the inpatient, non-IP, or pharmacy setting for doxorubicin hydrochloride, melphalan, bendamustine, cyclophosphamide, etoposide, or	MM diagnosis to 1 day prior to index date
		cisplatin (dichotomous)	Index date to the end of follow-up
1	Small molecule inhibitors	Medical claim with an NDC, HCPCS, generic name or CPT code in the inpatient, non-IP, or pharmacy setting for venetoclax (dichotomous)	MM diagnosis to 1 day before index date
		setting for venerociax (dichotomous)	Index date to the end of follow-up
1	Nuclear export inhibitors	Medical claim with an NDC, HCPCS, generic name or CPT code in the inpatient, non-IP, or pharmacy setting for selinexor (dichotomous)	MM diagnosis to 1 day before index date
		coming for community (controlled as)	Index date to the end of follow-up
1	Antivirals	Medical claim with an NDC, HCPCS, generic name or CPT code in the inpatient, non-IP, or pharmacy setting for antiviral medications (dichotomous)	14 days prior to index date to 1 day prior to index date

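### Objective 1 treatment history and time since diagnosis rest on claims guaranteed for only 180 days, so exposure before Medicare coverage is scored as absent and disease duration is understated

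*Protocol*

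**What the plan says.** Section 9.2 sets the window for prior MM treatment: "Baseline period for MM-related treatments and MM-related comorbidities: MM diagnosis to one day prior to index date". The search for the diagnosis is bounded by the data: "MM diagnosis window: Start of data (Jan 1, 2016) to index date". Table 1 defines the diagnosis as a medical claim with an MM code.

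Inclusion criterion 4 in section 9.2.1 guarantees much less: "At least 180 days of continuous closed-claims medical and pharmacy enrollment prior to index (inclusive) and 30 days post-index".

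Table 2 (section 9.3) makes triple-class exposure, penta-drug exposure, transplant, CAR-T and each drug class a yes/no variable, scored by whether a claim appears in that window. Time since diagnosis is a continuous variable running from the first MM diagnosis to index. IMiDs have the narrowest capture rule: "Medical claim with an NDC code or generic name in the non-IP or pharmacy setting for lenalidomide, thalidomide, or pomalidomide (dichotomous". The IMiD entry in Annex 2 shows no HCPCS codes, unlike the entries for PIs and CD38 antibodies.

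Section 9.7.1 gives missing categorical data their own category, but nothing defines absence of a claim as missing. Section 9.9 says that treatment not reimbursed by Medicare is unavailable. It does not connect this to baseline history or to disease duration.

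**The concern.** A yes/no history variable read from claims is only as complete as the period of coverage. Suppose a patient became entitled to Medicare by age, disability or ESRD some time after diagnosis, or took up Part D late. Earlier care was then paid for elsewhere. Under the Table 2 definitions, a class used only in that earlier period is scored no, exactly as if the patient had never received it. If the first diagnosis was also made before coverage, the first MM claim seen in Medicare stands in for the diagnosis date.

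Two results of a primary objective are affected. Exposure percentages are understated, and triple-class status is the most fragile because a single hidden class is enough to lose it. Time since diagnosis is shortened. A reader of the results could then conclude that the drug is given to less heavily pre-treated patients, or earlier in the disease, than is true. The planned entitlement subgroups in section 9.7 could also differ because their coverage histories differ. More patients would narrow the confidence intervals but would not reduce this error.

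**Working it through.** The protocol states no figure on this point, so there is none to reproduce.

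**1. Longest and shortest possible look-back.** Inputs: data start 1 January 2016 and index from 14 August 2023 to March 2025 (section 9.2; month-end assumed); 180 days of enrolment (section 9.2.1); 30.4375 days per month (section 9.7.5).

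- Index 14 August 2023: 2,782 days / 30.4375 = 91.4 months.
- Index 31 March 2025: 3,377 days / 30.4375 = 110.9 months.
- Guaranteed: 180 / 30.4375 = 5.9 months, which is 180/2,782 = 6.5% or 180/3,377 = 5.3% of the maximum.

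The upper figure uses the March 2025 index limit of section 9.2. Section 9.2.1 instead lets index run to the latest available data. With data to 31 December 2025 and 30 days required after index, the last index date would be 1 December 2025, and the cap 3,622 / 30.4375 = 119.0 months.

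**2. Who is misclassified.**

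- *Coverage from before the disease began, with Parts A, B and D throughout:* history is complete, apart from anything before 2016.
- *Parts A/B long, Part D recent:* the diagnosis date is kept, because diagnosis comes from medical claims. Earlier IMiD use can be lost, and triple-class status with it.
- *Medicare FFS itself began after diagnosis:* the diagnosis date moves later, and any class used only before coverage is scored no. A class used again during coverage is still scored yes, because one claim per class is enough for triple-class status.
- *Transplant* is partly protected. Annex 2 lists diagnosis codes as well as procedure codes, so a later claim may still reveal it.

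**3. Illustration of size (assumptions, not protocol figures).** Let s be the share of patients with incomplete look-back, and q the chance that all use of a given class precedes it. Take true triple-class exposure as 100% and the three classes as independent:

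observed exposure = 1 − s × [1 − (1 − q)³]

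| s | q = 0.25 | q = 0.50 | q = 0.75 |
|---|---|---|---|
| 10% | 94.2% | 91.2% | 90.2% |
| 20% | 88.4% | 82.5% | 80.3% |
| 40% | 76.9% | 65.0% | 60.6% |

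A milder set takes true exposure as 95%, with f = 10% to 30% of patients having short look-back and m = 30% to 70% of those losing at least one class. This gives 0.95 × (1 − 0.1 × 0.3) = 92.2% down to 0.95 × (1 − 0.3 × 0.7) = 75.0%.

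For scale, the 95% half-width at n = 133 (section 9.5) is 1.96 × √(p(1 − p)/133): 5.1 points at p = 0.9, 6.8 at 0.8 and 8.5 at 0.5. The mildest shift, about 3 points, lies inside sampling error. Most of the others exceed it.

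For duration, assume a true 60 months for everyone and s = 20% truncated at L months. The observed mean is 0.8 × 60 + 0.2 × L, which is 49.2 months at L = 5.9 and 55.2 at L = 36.

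**The case against.** Several counter-arguments are sound and limit the point.

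- **All available claims are used.** The 180 days is an entry floor, not the look-back. A reader might infer that history is taken from 180 days only. Section 9.2 does not say that, and searching everything back to 2016 is a legitimate choice.
- **The label is not the cohort.** Section 7 says "Elranatamab is approved in the US for patients who have received at least four lines of therapy". It is tempting to conclude that every patient here has four earlier lines that the data must recover. No inclusion criterion requires prior lines and no variable counts them; Table 2 records exposure to classes.
- **A 5.9-month limit on duration is not general.** It applies only to patients whose Medicare claims themselves began about 180 days before index.
- **Some protection exists.** Section 9.2.2 removes anyone with Medicare Advantage during the study period, and section 9.9 concedes that non-Medicare treatment is unseen.
- **Subgroups.** A reader might infer that disability, ESRD or newly 65 patients are distorted most. The protocol gives no entitlement durations, and newly 65 patients are not a separate subgroup, so this cannot be shown.
- **A restricted main analysis would be costly.** With 133 patients as of August 2024 and suppression of cells of 1 to 10 (section 9.4), reporting a long-look-back subset as the primary result could leave cells unreportable.

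What remains is that none of these separates not exposed from not observable. The Medicare Advantage exclusion does not reach time before entitlement, before 2016 or without Part D. Finer reporting could sit in the SAP, but the windows, the yes/no definitions and the limitations text are fixed in the protocol.

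**Conclusion.** The point holds as a defect in how Objective 1 history is defined and will be read. It is not an objection to the choice of window. Followed as written, the protocol scores unobservable exposure as no and reports truncated durations as complete. The truncation itself can only lower exposure and duration. Rule-out coding, which section 9.9 mentions, is a separate error.

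The cap of 91.4 to 110.9 months on time since diagnosis is firm, given the section 9.2 index dates. The size of the exposure bias is unknown. The range of 94% down to 61% rests entirely on assumed values for s and q, on independence between classes and on a true value of 100%. It shows only that the bias could range from negligible to larger than sampling error at n = 133. The change is worth making because this is a primary objective and the data needed to judge completeness are already held.

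**What to change.** Keep the 180-day entry rule and the all-available-data window as the main analysis. Then:

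1. Derive each patient's observable Part A/B look-back and Part D look-back, and report both distributions overall and by entitlement subgroup.
2. Label all-patient exposure percentages and time since diagnosis as *observed in available claims (minimum)*.
3. Add a sensitivity analysis of the history variables in patients with a longer, prespecified continuous Part A/B/D look-back, choosing the threshold so that cells stay above the CMS limit.
4. Report duration as *at least x months* when the first C90.0x claim is not preceded by a prespecified enrolled period free of MM claims.
5. State left truncation of treatment history and disease duration in section 9.9.

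The cost is small. Section 9.6 already places enrolment dates in the analytic file, so the work is a few derived variables, one extra analysis and some wording. The drawback is smaller denominators, and so wider intervals, in the sensitivity analysis.
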